3.0 Project Procedures

This will be a randomized pragmatic study for all patients ages 6-17 years with simple lacerations. Simple lacerations will be defined as lacerations within the scope of pediatric emergency medicine providers AND not requiring sedation or operative intervention. Subjects will be identified by the Emergency Department staff for enrollment. The goal number of enrolled participants will be 480, including 240 patients randomized into two groups, 120 per group, and 240 parents/guardians. The Emergency Department accepted to participate in this study and ED providers will complete the provider's survey. After signing the consent and assent form when appropriate, the patients will be randomized to either receive the standard of care or standard of care with immersive virtual reality goggles. Consent and assent will be obtained in the patient rooms within the emergency department. The standard of care shall be defined to include any of the following: local analgesia (topical LET and/ or subcutaneous lidocaine), oral or intranasal midazolam, distraction, Child Life Staff, or physical holding. Because each of the aforementioned interventions may vary between patients, it cannot be truly standardized; hence, this will be considered a pragmatic study. Patients randomized to the VR arm will receive the other standard procedures as well with VR goggles as an adjunct. Exclusion criteria include a history of epilepsy, visual or hearing impairment, or intellectual disability that would preclude use of VR goggles as determined by the guardian. Additionally, any lacerations around the eyes, eyebrows, and nose will be excluded as well as patients requiring sedation. Non-English speaking patients will be excluded as well. Hand lacerations will not be excluded.

Participants will be identified by ED staff following evaluation of the laceration. The ED staff will be given a flowchart with eligibility criteria. All interested participants who meet eligibility criteria will be consented. A research team member will obtain consent from parents or guardians by providing and reviewing the consent form (see Subject Consent Form). For patients who are between 8 and 17 years of age, a research team member will obtain assent by providing and reviewing the assent form (see Subject Assent Form). Consent and assent will be obtained in the patient's ED room.

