Patients will be separated into groups age 6-11 and 12-17. Patients will be randomized via a selection of a sealed envelope which will contain instructions for use of the VR goggles. The goggles utilized will be Lenovo Mirage Solo with DayDream, which are standalone VR headset with WorldSense Body Tracking. Research staff will coach the child on age-appropriate games, as previously determined by Lenovo.

The goggles will be cleansed with Oxivir Tb disinfectant wipes after each use and allowed to dry in room air prior to next use. Education will be provided to all ED providers on the proper cleansing protocol for the VR goggles (Figure 4). The disinfectant protocol will be available for all users during the study, and has been approved by the director of Infection Control at Children's Hospital of the King's Daughters.

Following the laceration repair, the patient, guardian and health care provider will be surveyed (Figure 1, 2, and 3) on paper surveys. The survey includes Likert-type scale questions, binary

questions as well as incorporates the Wong Baker Faces Pain Scale and Children's Fear Scale. The duration of the procedure will be recorded by the healthcare provider who completed the laceration repair. Time of procedure will be defined as from the time of irrigation to wound dressing. Patients and parents will both be filling out their own individual surveys. The parent should complete the survey first before the child should the child need assistance with completion. Patients and parents may decline to participate in any survey at any time.

The recruitment period will be from November 2021 until February 2021. Enrolled participants will not be compensated, and enrollment will be completely voluntary.

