4.0 Statistical Analysis

Continuous variables will be presented as mean, standard deviation, median, 25th, and 75th percentile. Categorical variables will be presented as frequency and percentage. Generalized Linear Model (GLM) will be used to assess the effect of intervention on the outcomes of the surveys. The correlation between provider's, parent's, patient's survey will be analyzed using the Spearman's correlation test. All statistical tests will be performed using the R software. All statistical tests will be 2-sided and $p < 0.05$ will be considered as statistically significant.

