6.0 Budget

The Virtual Reality goggles are property of the Children's Hospital of the King's Daughters Child Life department. They will be stored in a locked drawer within the CHKD Emergency Department. This project is unfunded.

Figure 1. Use of Immersive Virtual Reality for Laceration Repairs in the Pediatric Emergency
Department
Patient Survey

1. How old are you? _____

2. Have you had stitches before? Yes
 No
 Unsure

3. Have you ever used Virtual Reality (VR) goggles before today? Yes
 No
 Unsure

4. Did you use VR goggles for your stitches today? Yes
 No

5. Would you use VR goggles again to get stitches? Yes
 No

6. During your stitches, did you have any of the following (select all that apply)?
 I did not experience any symptoms
 Dizziness
 Headache
 Nausea
 Vomiting
 Other (describe below)

7. How do you think the stitches went overall? Not well at all
 Somewhat not well
 Neutral
 Somewhat well
 Very well

8. The virtual reality goggles made the stitches seem less scary.
 Strongly disagree
 Disagree
 Neutral
 Agree
 Strongly agree

9. How would you rate your pain:

10. How would you rate how scared you were during the stitches:

[figure not shown]

Figure 2. Use of Immersive Virtual Reality for Laceration Repairs in the Pediatric Emergency
Department
Guardian Survey

1. **Patient Gender:**

Male
 Female
 Non-binary
 Self-identify
 Prefer not to say

2. What is the patient's age? _____

3. Please indicate if the patient has a developmental disability:

A. The patient does not have a developmental disability
B. Autism
C. Cerebral Palsy
D. Intellectual disability
E. Speech delay
F. _____

4. Has the patient had stitches previously? _____

Yes
 No
 Unsure

5. Has the patient ever used Virtual Reality (VR) goggles before today? _____

Yes
 No
 Unsure

6. Did the patient use VR goggles for the procedure today? _____

Yes
 No

7. If, yes, would you use VR goggles again for this procedure? _____

Yes
 No
 Did not use today

8. During the procedure did the patient experience any symptoms (select all that apply)?

Did not experience any symptoms
 Dizziness
 Headache
 Nausea
 Vomiting
 Other (*describe below*)

9. How do you think the procedure went overall?

- Not well at all
- Somewhat not well
- Neutral
- Somewhat well
- Very well

10. In your opinion, did the virtual reality goggles make the procedure seem less scary to the patient?

[figure not shown]
- Strongly disagree
- Disagree
- Neutral
- Agree
- Strongly agree

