11. How would you rate the patient's pain:

Wong-Baker FACES® Pain Rating Scale

12. How would you rate the patient's fear:

No fear A little fear Some fear A lot of fear The most fear

Figure 3. Use of Immersive Virtual Reality for Laceration Repairs in the Pediatric Emergency
Department
Provider Survey

1. Procedure Duration (*from irrigation to closure end*):
A. <10 minutes
B. 10-15 minutes
C. 16-20 minutes
D. 21-25 minutes
E. >25 minutes

2. Did the patient use VR goggles for the procedure today?
 Yes
 No

3. Would you recommend VR goggles again for this procedure?
 Yes
 No

4. Did the patient need to be held during the procedure?
 Yes
 No

5. Did the patient receive medicine intended to help them stay calm?
 Yes
 No

6. During the procedure, did the patient experience any symptoms (select all that apply)?
 Did not experience any symptoms
 Dizziness
 Headache
 Nausea
 Vomiting
 Other (*describe below*)

7. How do you think the procedure went overall?
 Not well at all
 Somewhat not well
 Neutral
 Somewhat well
 Very well

8. In your opinion, did the virtual reality goggles make the procedure seem less scary to the patient?

Strongly disagree
 Disagree
 Neutral
 Agree
 Strongly agree

9. How would you rate the patient's pain:

10. How would you rate the patient's fear:

[figure not shown]

Figure 4. Education Plan for Disinfection Protocol for Virtual Reality Goggles

1. The company insert for cleansing the virtual reality goggles will be printed, laminated, and physically located with the goggles in their carrying case.
2. The protocol for cleaning will be addressed during an Emergency Medicine division meeting prior to the start of the project and detailed in the meeting minutes.
3. The protocol will be addressed during a pediatrics monthly resident meeting and dispersed in an email from the chief residents.
4. The protocol will be emailed to all rotating residents prior to the start of their rotation.
5. The protocol will also be disseminated to nursing staff and ED techs via [name] prior to the start of the project.
6. Research project staff will be available either in person or by phone to answer any questions regarding the disinfection protocol during the study phase of the project. Contact information will be included inside the carrying case for the goggles as well as on all written communications (division meeting minutes, chief email, etc.)

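### Patients are split into ages 6-11 and 12-17 just before randomisation for no stated purpose, and the only model sentence names the intervention alone; adding age group is a small gain at almost no cost.

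*Combined protocol and SAP*

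**What the plan says.** Section 3.0 (Project Procedures) sets enrolment at "240 patients randomized into two groups, 120 per group". Later in the section comes "Patients will be separated into groups age 6-11 and 12-17", followed at once by "Patients will be randomized via a selection of a sealed envelope which will contain instructions for use of the VR goggles". The same paragraph adds "Research staff will coach the child on age-appropriate games, as previously determined by Lenovo", but does not tie the games to the two age groups. The section does not mention strata, blocks or separate envelope sets by age.

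Section 4.0 (Statistical Analysis) has one sentence on the model: "Generalized Linear Model (GLM) will be used to assess the effect of intervention on the outcomes of the surveys". It gives no covariate, family or link, and age does not appear in the section. Tests are two-sided at 0.05.

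Age is collected. The patient survey (Figure 1) asks "How old are you", and the guardian survey (Figure 2) asks it too.

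**The concern.** The age split could be a randomisation stratum, a way to choose games, or a plan to analyse the two age groups separately. The text does not settle which, and Section 4.0 gives the analyst no instruction about age. Three different primary analyses would fit the plan: arm only, arm with age group, or one comparison per age group.

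What is at stake is precision, not validity. In a linear model of the pain or fear score:

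- **Arm only, allocation not forced to balance within age groups** (simple randomisation within groups, or one unstratified envelope set): the standard error is valid but larger than necessary.
- **Arm only, allocation forced to balance within age groups** (blocks or fixed counts): the model-based standard error is also too large for the design, so the test is conservative.
- **Separate analyses by age:** each uses only part of the sample. This would cost more power than leaving age out at any age gap considered here.

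**Working it through.** **Inputs from the documents.** 240 patients, 120 per arm (Section 3.0); two-sided 0.05 (Section 4.0); pain and fear scores as primary outcomes (Section 2.0). The counts agree: 2 × 120 = 240 patients, and 240 + 240 guardians = 480. No power, effect size or SD is given, so the 120 per arm cannot be re-derived.

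**Assumed inputs.** Age gap d between the two groups, in within-group SD: 0 to 0.8. Share p aged 6-11: 0.5, with 0.7 as a check. Arm effect: the one that gives the model with age group 80% power, about 0.363 SD.

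**Formulas (linear model).** Let k be the standard error without age group divided by the standard error with it.

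- k = sqrt(1 + p(1−p)d²); fall in SE from adding age group = 1 − 1/k
- Balance not forced: size 0.05; arm-only power = Φ(2.80/k − 1.96)
- Balance forced within age groups: size = 2(1 − Φ(1.96k)); arm-only power = Φ(2.80 − 1.96k)

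Example, d = 0.5 and p = 0.5: k = sqrt(1 + 0.25 × 0.25) = sqrt(1.0625) = 1.031, so the SE falls by 1 − 1/1.031 = 3.0%.

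| Age gap (SD) | k, 50:50 | SE fall, 50:50 | SE fall, 70:30 | Arm-only power, not forced (50:50) | Arm-only power, forced (50:50) | Size, forced (50:50) |
|---|---|---|---|---|---|---|
| 0 | 1.000 | 0% | 0% | 80% | 80% | 5% |
| 0.2 | 1.005 | 0.5% | 0.4% | 79.6% | 79.7% | 4.9% |
| 0.3 | 1.011 | 1.1% | 0.9% | 79.1% | 79.4% | 4.7% |
| 0.5 | 1.031 | 3.0% | 2.5% | 77.6% | 78.3% | 4.3% |
| 0.8 | 1.077 | 7.2% | 6.1% | 73.9% | 75.5% | 3.5% |

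**Simulation** (20,000 trials per scenario, 240 patients, 50:50 age, arm effect 0 or 0.363 SD). Results are for the arm-only model, with power for the model with age group in brackets.

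| Allocation | Age gap (SD) | Size | Power |
|---|---|---|---|
| Blocks of 4 within age groups | 0.5 | 4.3% | 78.3% (79.9%) |
| Blocks of 4 within age groups | 0.8 | 3.5% | 75.5% (80.0%) |
| Simple, within age groups | 0.5 | 5.0% | 77.4% (79.8%) |
| Simple, within age groups | 0.8 | 5.1% | 73.6% (79.7%) |
| One unstratified 120/120 set | 0.5 | 4.7% | 78.2% (80.6%) |
| One unstratified 120/120 set | 0.8 | 5.0% | 74.3% (80.3%) |

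Under blocking the mean model SE exceeds the empirical SE (0.133 against 0.129 at 0.5 SD; 0.139 against 0.130 at 0.8 SD). Under simple randomisation they agree (0.133 and 0.133; 0.139 and 0.140).

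**The same question from the other side.** Start from 80% power for the arm-only model and let age group explain a share R² of the variance. Adding it gives 80.4, 80.8, 82.0 and 84.0% power at R² = 0.01, 0.02, 0.05 and 0.10. The effective sample is 120/(1 − R²) per arm, so 126 at R² = 0.05 and 133 at 0.10. A separate simulation with allocation balanced within age groups put the size of the arm-only test at 4.5% and 3.8% for these two values, and at 5.1% and 5.0% with age group in the model.

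**Five-category score.** The fear item has five levels ("No fear A little fear Some fear A lot of fear The most fear"). A latent normal cut at −0.2, 0.4, 1.0 and 1.6 (assumed) and fitted with a linear model (8,000 trials, simple randomisation) gave SE changes of +0.2, −2.3 and −6.2% at gaps of 0, 0.5 and 0.8 SD. The mean arm estimate hardly moved: −0.406 without and −0.405 with age group at 0.5 SD, and −0.413 and −0.414 at 0.8 SD.

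**Separate analyses by age** (two-sample t-test).

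| Patients per arm | Difference detectable at 80% power | Power at 0.363 SD |
|---|---|---|
| 120 (all) | 0.363 SD | 80.0% |
| 60 (each group, 50:50) | 0.516 SD | 50.5% |
| 84 (larger group, 70:30) | 0.435 SD | 64.8% |
| 36 (smaller group, 70:30) | 0.670 SD | 33.0% |

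**The case against.** The strongest reply is that nothing is wrong, only improvable. An arm-only linear model is valid or slightly conservative, and Section 4.0 does not rule covariates out. The gain depends wholly on an age effect that the documents do not give. At 0.2 or 0.3 SD the power lost is under one percentage point. A gap of 0.8 SD means age group explains 0.16/1.16, or about 14%, of the variance, and nothing in the documents supports so large an effect. The separate-analysis reading also has little support: Section 2.0 states one objective, Section 3.0 gives 120 per arm, and Section 4.0 speaks of a single effect of intervention.

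All of this stands as a limit on size, and the largest figures, those for separate analyses, should not carry the case. It does not count against the change, which helps if age matters and costs next to nothing if it does not.

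Three further limits are fair. The plan names no link, and with a non-identity link these figures, including the absence of bias, need not carry over. Pain and fear are rated by patient, guardian and provider, and the plan does not say whose rating is primary. The provider survey (Figure 3) does not ask age, so those ratings must be linked by the unique study number in Section 5.0. The first two are separate gaps that the age-group sentence does not close. Age in years would be a reasonable alternative covariate if the two groups are not strata.

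**Conclusion.** The point holds as a modest improvement. The plan forms two age groups immediately before randomisation, gives no reason, and has a model sentence that does not mention age. For a linear model with 120 per arm and a 50:50 age split, adding age group lowers the standard error by 0.5 to 7.2% over assumed age gaps of 0.2 to 0.8 SD. Leaving it out costs about 0.4 to 6 points of power when balance within age groups is not forced, and about 0.3 to 4.5 points when it is. The test is conservative only in the forced case, and the text does not establish that case. The change should be made because it is nearly free and fixes the primary model before data are seen; the trial's validity does not depend on it.

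**What to change.** Add to Section 4.0: *The primary model for each of the pain and fear scores contains randomised arm and age group (6-11, 12-17), with one arm effect estimated over all patients.* The last clause also rules out two separate age-group analyses as the primary result.

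In Section 3.0, as a clarification, say whether the two age groups are randomisation strata and, if so, whether allocation is balanced within them by blocks or fixed counts.

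The cost is one sentence in the analysis section and no new data. Age is known before the envelope is opened, since eligibility, assent and the grouping itself depend on it. If age does not predict the scores, the standard error rises by about 0.2%.

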5.0 Risks to Participants/ HIPAA Privacy Considerations

No personal identifiers will be recorded as part of the research study. Each enrolled participant will be given a unique number for data collection purposes. The risks involved in the study include adverse reactions to the VR goggles, which have been described to rarely cause nausea, vomiting, and motion sickness. There is a theoretical infection risk, but the VR goggles will be cleaned following a decontamination protocol following each use.

The data will be securely stored in RedCAP without any patient identifiers. The paper surveys will be kept in a locked drawer in a locked room within the Pediatric Department of Emergency Medicine offices.

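### The envelope procedure fixes no order of use and describes no concealment steps, so an envelope could be chosen or re-drawn and the resulting imbalance could not be fully corrected

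*Combined protocol and SAP*

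**What the plan says.** Everything the plan says about allocation is in section 3.0 (Project Procedures).

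- **Method:** "Patients will be randomized via a selection of a sealed envelope which will contain instructions for use of the VR goggles".
- **Timing:** "After signing the consent and assent form when appropriate, the patients will be randomized to either receive the standard of care", or standard care plus the goggles.
- **People:** "Participants will be identified by ED staff following evaluation of the laceration", and "A research team member will obtain consent from parents or guardians by providing and reviewing the consent form". Consent is taken in the child's ED room. Who selects the envelope is not stated.
- **Numbers:** "including 240 patients randomized into two groups, 120 per group, and 240 parents/guardians".
- **Age:** "Patients will be separated into groups age 6-11 and 12-17". The next sentence turns to envelopes without saying that each age group has its own set.
- **Treatment:** "Patients randomized to the VR arm will receive the other standard procedures as well with VR goggles as an adjunct". No sham headset or other blinding is described.

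Section 5.0 adds "The data will be securely stored in RedCAP without any patient identifiers", but says nothing of randomisation through that system. Section 4.0 (Statistical Analysis) plans a generalized linear model for the intervention effect and names no covariate.

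**The concern.** Concealment depends on nobody being able to know or change the next assignment once a particular child is in view. Sealing an envelope helps, but it does not determine which envelope is used next. Selecting an envelope is compatible with choosing from a pile, putting one back or opening a second. The plan describes no numbering, fixed order or log that would prevent this or show it afterwards.

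Three features of this trial raise the stakes.

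- By the time of allocation the laceration has been evaluated and consent taken at the bedside, so people near the child have had the chance to see how distressed the child is.
- The headset is visible, so past allocations are known.
- All surveys are completed after the repair, and none asks for pain or fear beforehand. The forms in Figures 1 to 3 ask whether goggles were used, not which arm was assigned.

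If calmer children tended to be placed in one arm, their lower expected scores would appear as a treatment effect. The data would hold no baseline distress measure with which to see or fully correct it.

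**Working it through.** **Step 1: the plan's own figures.** 2 × 120 = 240 patients, and 240 + 240 parents/guardians = 480, which agrees with section 3.0. The plan gives no effect size, SD or power, and no figure for allocation, so there is nothing further to reproduce.

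**Step 2: what is and is not described.**

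| Element | In the plan? |
|---|---|
| Sealed envelope | Yes |
| Randomisation after consent | Yes |
| Two groups of 120 | Yes |
| How the sequence is generated; blocking | No |
| Fixed order of use; numbering | No |
| Opacity; identical appearance | No |
| Who prepares, holds and selects | No |
| Contents of a control envelope | Unclear |
| Separate sequence per age group | No |
| Opening log | No |

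The contents can be read in two ways. Every envelope may hold a sheet saying whether to use the goggles, or only VR envelopes may hold a VR sheet. The arms could be told apart by feel or look only under the second reading. Free choice of envelope is possible under both.

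**Step 3: illustrative size.** From the documents: 120 per arm (section 3.0) and a two-sided 0.05 level (section 4.0). Assumed, with no support in the documents: a fraction *f* of patients is steered, all in one direction; steered patients sent to VR differ by *g* SD in expected outcome from those sent to control; the true effect is zero.

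- Bias = *f* × *g* (in SD)
- SE of the arm difference = √(2/120) = 0.129 SD
- Type I error = P(|Z + bias/SE| > 1.96)

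| *f* | *g* (SD) | Bias (SD) | Bias/SE | Type I error |
|---|---|---|---|---|
| 0 | any | 0 | 0 | 5.0% |
| 5% | 0.5 | 0.025 | 0.19 | 5.4% |
| 10% | 0.5 | 0.05 | 0.39 | 6.7% |
| 10% | 1 | 0.10 | 0.77 | 12.1% |
| 20% | 1 | 0.20 | 1.55 | 34.1% |

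**Step 4: how demanding those inputs are.** Suppose steering sends children with a better-than-median expected outcome to VR, judged on an impression that correlates ρ with the outcome. Then *g* = 2√(2/π) × ρ = 1.596ρ. So *g* = 0.5 needs ρ = 0.5/1.596 = 0.31, and *g* = 1 needs ρ = 1/1.596 = 0.63. Type I error by share steered:

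| ρ | 5% | 10% | 20% | 30% |
|---|---|---|---|---|
| 0.3 | 5.4% | 6.6% | 11.5% | 19.9% |
| 0.5 | 6.1% | 9.5% | 23.5% | 45.8% |

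For scale, 120 per arm detects (1.96 + 0.84) × 0.129 = 0.36 SD with 80% power.

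**Step 5: predictability under the remedy.** Blocking has its own cost in an unblinded trial. Suppose someone knows a fixed block size and all past allocations, guesses the arm with more places left, and guesses at random when tied. Simulation gives 75% correct guesses with blocks of 2, 71% with blocks of 4, 68% with blocks of 6, and 54% with one block of 240. This is why block sizes should vary and stay undisclosed.

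**The case against.** The strongest reply is that this is a reporting gap. Envelopes are sealed, allocation comes after consent, and the people who identify patients are not described as those who take consent. Two groups of exactly 120 suggest a set prepared in advance, and the wording fits drawing from a shuffled or ordered stack. All of that lowers the risk and should be credited. It does not establish concealment, because nothing fixes which envelope comes next or records what was opened.

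Several further objections stand. A reader might infer that no sequence exists, or that enrolling staff choose the envelope; the documents say neither, only that no sequence and no selector are described. A reader might also infer that the arms can be told apart by feel, but that depends on one reading of the contents. The higher error rates need a strong impression of the child and consistent steering; motives pulling in opposite directions would partly cancel. Some adjustment is possible, since age and previous stitches are collected, though neither measures distress on the day. Finally, steering on prognosis would bias objective outcomes too, so the subjectivity of the pain and fear scores is not the reason for this concern.

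**Conclusion.** The point holds as a statement of what the stated method permits. Section 3.0 describes an allocation step that allows choosing or re-drawing an envelope and, on one reading, recognising its arm. Imbalance in distress could then be neither detected nor fully adjusted for. The size cannot be known from the documents. On the assumptions above, type I error is about 5% to 7% with mild steering and 12% or more with strong, one-directional steering. These figures rest on assumed shares, assumed prognostic gaps, 120 analysed per arm and a normal approximation.

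A reader might take the highest rates as the expected error of this trial, or as a sign that steering took place. The documents support neither: they give no information on any *f* or *g*. The change is worth making because the exposure is cheap to close beforehand and cannot be fully repaired later.

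**What to change.** Replace the allocation sentence in section 3.0 with text to this effect:

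*Allocation is 1:1 from a computer-generated list, stratified by age group (6-11, 12-17), in randomly permuted blocks of varying, undisclosed size, prepared by someone not involved in enrolment. Each assignment is released only after consent (and assent where required) and after the study number has been recorded. Assignments are held in opaque, identical envelopes, numbered sequentially within age group and opened in order. Every envelope contains an arm sheet of the same size. Each opening is entered in a log.*

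Keep the VR instructions with the headset, not in the envelope. If the REDCap randomisation module is available at the bedside, it can replace the envelopes. The plan documents REDCap only for data storage, so access has to be confirmed. In section 4.0, include age group in the GLM to match the stratification. If the site already works this way, the change is only to write it down.

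The cost is preparing the list and envelopes and revising a few sentences. Staff must handle two envelope stacks, or log in at enrolment, and blocking leaves slight residual predictability. Rating bias from lack of blinding is a separate matter that this change does not remove.

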2.0 Objectives

The objective of this study is to determine if VR goggles can decrease patient pain and anxiety during simple laceration repairs. The primary outcome will be pain scores as assessed by the validated Wong Baker Faces Scale and anxiety scores as assessed by the validated Children's Fear Scale. A validated System Usability Scale (SUS) will be measured for each enrolled participant that used the VR goggles. Secondary outcomes include time of procedure, use of physical holding, adverse outcomes, and pharmacologic interventions.

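### No form identifies the repairing provider, so repeated ratings by one provider cannot be allowed for in the provider correlations or the provider-supplied outcomes.

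*Combined protocol and SAP*

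**What the plan says.** Section 3.0 sets the target: "The goal number of enrolled participants will be 480, including 240 patients randomized into two groups, 120 per group, and 240 parents/guardians". Providers are not in that count. The same section says "ED providers will complete the provider's survey", and that "The duration of the procedure will be recorded by the healthcare provider who completed the laceration repair".

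Section 2.0 lists the secondary outcomes: "Secondary outcomes include time of procedure, use of physical holding, adverse outcomes, and pharmacologic interventions". Figure 3 has an item on each of them. Duration (item 1, five bands), holding (item 4, "Did the patient need to be held during the procedure") and calming medicine (item 5) are asked only of the provider. Symptoms (item 6) also appear on the patient and guardian forms. Items 9 and 10 are the provider's ratings of the child's pain and fear. None of the ten items asks who the provider is or at what training level, and Figures 1 and 2 do not ask either. Section 5.0 gives a unique number to enrolled participants only.

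Section 4.0 plans a GLM to "assess the effect of intervention on the outcomes of the surveys" and Spearman correlations among the provider, parent and patient surveys, two-sided at 0.05. It names no provider term and no allowance for clustering.

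**The concern.** A provider who repairs several children brings the same habits to each of them: pace, readiness to hold a child or give calming medicine, and leniency in rating pain and fear. Section 3.0 leaves care unstandardised on purpose, so such habits have room to show.

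Two analyses are touched. In the arm comparison of provider-supplied outcomes, differences between providers stay in the residual variance and cannot be removed. In the correlations, ratings by one provider are counted as independent pieces of information when they may not be. The forms are on paper and carry no provider field, and the plan describes no way to recover the provider later. What is not collected may be lost.

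**Working it through.** **Inputs from the plan.** There are 240 patients, 120 per arm, tested two-sided at 0.05. The counts agree (2 × 120 = 240; 240 + 240 = 480). The plan states no effect size, SD or power, so there is no power figure to reproduce.

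**Assumptions, not in the plan.** I take 20 to 60 providers, hence m = 240/60 = 4 to 240/20 = 12 repairs each. The intraclass correlation (ICC) is 0.05 to 0.2. Provider shares of variance are 0.1-0.2 in the child's score and 0.2-0.3 in the provider's.

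**1. Validity of the VR comparison.** Children are randomised individually. In simulation with 20 or 40 providers and ICC 0.05 to 0.2, the analysis that ignores provider kept a type I error of 4.8-5.6%. The issue is precision, not bias.

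**2. Precision on a linear provider-supplied outcome.** With m repairs per provider, the variance of the unadjusted difference divided by that with a provider random intercept is approximately

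[1/(1 − ICC)] × [1 + (m − 2) ICC] / [1 + (m − 1) ICC].

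- ICC 0.05: m = 4 gives (1/0.95) × (1.10/1.15) = 1.01; m = 12 gives (1/0.95) × (1.50/1.55) = 1.02.
- ICC 0.1: m = 4 gives (1/0.9) × (1.2/1.3) = 1.03; m = 12 gives (1/0.9) × (2.0/2.1) = 1.06.
- ICC 0.2: m = 4 gives 1.25 × (1.4/1.6) = 1.09; m = 12 gives 1.25 × (3.0/3.2) = 1.17.

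The random intercept therefore acts like 1-2%, 3-6% and 9-17% more patients. Simulation agrees.

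**3. Random or fixed provider effects.** At the difference that gives 80% power unadjusted (0.362 SD), fixed effects with 40 providers gave simulated power of 75% at ICC 0.05 and 78% at 0.1. Fixed effects can cost more than they recover.

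**4. The Spearman test.** Suppose there is no true link and the provider shares are s_c in the child's score and s_p in the provider's. The variance of the correlation is then inflated by about 1 + (m − 1) s_c s_p.

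- Mildest case, m = 4, shares 0.1 and 0.2: 1 + 3 × 0.02 = 1.06. The test uses 1.96/√1.06 = 1.90, a false-positive rate of about 6%.
- Strongest case, m = 12, shares 0.2 and 0.3: 1 + 11 × 0.06 = 1.66. The test uses 1.96/√1.66 = 1.52, about 13% by this approximation and about 12% by simulation.
- If the provider effect sits in one of the two scores only, the product is zero and the simulated rate stays near 5%.

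**5. Size of the pooled correlation.** Take a within-provider correlation of 0.60, shares 0.10 and 0.20, and let rho be the correlation between the provider's effects on the two scores:

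pooled r = 0.60 × √(0.90 × 0.80) + rho × √(0.10 × 0.20) = 0.509 + 0.141 × rho.

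This gives 0.51 at rho = 0, 0.60 at rho = 0.64 and 0.65 at rho = 1. With leniency in the provider's rating only (share 0.20), it is 0.60 × √0.80 = 0.54.

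**The case against.** The strongest reply is that individual randomisation balances providers in expectation, that the p-value already covers chance imbalance, and that the trial is pragmatic by design. For the VR comparison this stands. A reader might infer that ignoring provider biases that comparison; nothing in the plan or the simulation supports that.

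A reader might also infer that the provider-child correlation is understated. That holds if providers differ only in leniency. If a provider whose repairs hurt more also rates pain higher, the pooled value can exceed the within-provider one, so the direction is open. Pooled agreement, leniency included, is also a legitimate target. The case is for reporting both, with a sound interval.

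The precision figures are for a mean difference in a linear model. Duration is banded, and holding and medicine are yes/no. A logistic or ordinal random-intercept model estimates an odds ratio conditional on provider, so the figures do not carry over directly. They also do not describe the child's own pain and fear scores.

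It is tempting to state that trainees and senior staff share the repairs. The nearest support is Figure 4, item 4, on goggle cleaning: "The protocol will be emailed to all rotating residents prior to the start of their rotation". It does not say that residents repair lacerations, so a mix of training levels is an inference.

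Finally, a test against zero may matter little: at an underlying correlation of 0.60, every simulated test was significant. That is fair. The estimate and its interval are then what the clustering affects.

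**Conclusion.** The point holds in a limited form. The plan collects several outcomes from the repairing provider and tests the provider's ratings against those of others, yet records nothing that would link ratings made by the same provider.

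- **VR comparison:** valid as planned, with some avoidable loss of precision on provider-supplied outcomes. The loss is small at an ICC of 0.05-0.1 and moderate at 0.2.
- **Provider-patient and provider-parent correlations:** p-values can be too small when both scores carry provider effects, and the pooled value may lie above or below the within-provider one. The provider-parent figure assumes that the parent's score carries a provider share like the child's.

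All sizes rest on assumed provider numbers, ICCs and shares, because the plan gives none. This is worth correcting because the change is cheap and may not be possible after data collection. It does not threaten the main conclusion.

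**What to change.** **Figure 3.** Add an anonymous provider code and a training-level tick box. Fill in both before the envelope is opened, so that they cannot depend on the arm. If someone else then does the repair, add that provider's code too, since the correlations need the actual rater.

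**Section 4.0.** Add a provider random intercept, not fixed effects, to the models for duration, holding, calming medicine and provider-rated pain and fear. For banded and yes/no outcomes, say whether the reported effect is conditional on provider or marginal. Tabulate training level by arm. Report the provider-child and provider-parent correlations with provider-clustered confidence intervals, for example from a cluster bootstrap, and give the within-provider correlation beside the pooled one.

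**Cost.** Two fields on a paper form and a little more analysis in R. A list linking codes to staff must be held securely during the study, apart from the data. Section 5.0 says that no personal identifiers are recorded, so it should say how this list is kept.
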